13.4 Data Security and Confidentiality

During the course of the trial, user access to the files with subject identifiers, and files with study outcomes will be restricted to core staff with any exceptions to be approved by the Executive Committee.

In addition to use of passwords and other security measures, all documents containing identifying information on individuals or physicians are considered confidential materials and will be safeguarded to the greatest possible extent. No information, which identifies a specific person, hospital, or physician, will be released to, or discussed with anyone other than study staff members.

Because the DCU uses a web-based system, source documents and CRFs will remain at the participating sites. The study database only identifies study subjects by unique study identification codes. All data will be stored in a manner that is HIPAA compliant, without the ability to track the information back to a specific subject except through a password protected system. All collected information about a subject will be stored by a unique identification code. All DCU personnel have completed human subject protection training and good clinical practice training.

13.5 Data Quality Assurance

Upon entry of CRFs into the study database, quality control procedures will be applied at each stage of data handling in order to ensure compliance with GCP guidelines, integrity of the study data and document processing system reliability. These procedures are outlined in the Data Management Plan study document.

14. ADVERSE EVENT REPORTING

14.1 Definition of Adverse Events and Serious Adverse Events

An Adverse Event (AE) is any unfavorable and unintended sign, symptom, or disease temporally associated with the use of a medical treatment, device, or procedure regardless of whether it is considered related to the medical treatment, device, or procedures (attribution of unrelated, unlikely, possible, probable, or definite). (For example, hyperventilation and dizziness during phlebotomy procedures) A Serious Adverse Event (SAE) is any adverse event that results in any of the following:

- a) Death
- b) In-patient hospitalization (for reasons other than observation) or prolongation of an existing hospitalization
- c) A persistent or significant disability or incapacity
- d) Congenital anomaly/birth defects

The attribution of an AE or SAE characterizes its causal relationship to the study-related intervention/procedure as follows:

- a) Not Related
- b) Unlikely
- c) Reasonable Possibility
- d) Definitely

The study will utilize the version of the NCI Common Terminology Criteria for Adverse Events (CTCAE) for Toxicity and Adverse Event reporting that is specified in the protocol. A copy of the CTCAE Criteria can be downloaded from the CTEP home page (<http://ctep.info.nih.gov>).

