11. RISKS TO SUBJECTS

Randomization: Subjects will be assigned to receive the EUS + ERCP with miES procedure or EUS + sham procedure by chance. One treatment group may prove to be less beneficial or have more risks than the other group.

Blinding: To keep the study free from bias, the protocol has been carefully developed to minimize the risk of unmasking subjects and investigators responsible for evaluating subjects during follow-up. If a subject develops a medical problem where it is important for treating providers to know whether or not an ERCP was performed, there will be a mechanism in place for urgent unmasking of treating providers through the Statistical and Data Coordination Center (SDCC).

Sham: Subjects in the sham group will not receive ERCP with sphincterotomy. While these subjects will not be exposed to the risks specific to ERCP, including post-ERCP pancreatitis, subjects will not receive the potential benefit which may occur from the ERCP procedure.

Endoscopic ultrasound (EUS): All subjects will undergo EUS to evaluate for etiologies of RAP. The risks of EUS are similar to a standard esophagogastroduodenoscopy and

include perforation (<0.1%) and sedation-related cardiopulmonary complications (0.1-0.5%). EUS is a routine diagnostic test performed in clinical practice for patients with iRAP.

(ERCP) with minor papilla endoscopic sphincterotomy (miES): If randomized to ERCP with miES (approximately 50% of subjects), the procedure will be performed immediately after EUS and under the same anesthetic. Subjects undergoing ERCP with miES will be at-risk for the ERCP-specific complications which include post-ERCP pancreatitis (10-20%), post-miES hemorrhage (1-2%), and post-sphincterotomy perforation (<1%). The use of duodenoscopes has a very small risk of bacterial transmission (fewer than 100 reported cases of resistant infections potentially or definitely transmitted from duodenoscopes over many years, with approximately 500,000 ERCPs performed each year in the U.S.). Echoendoscopes used to perform EUS (see above), have a similar elevator mechanism but the risk of bacterial transmission from echoendoscopes has not been defined. ERCP with miES is performed for many patients with pancreas divisum and participation in this study will not expose them to a higher risk of ERCP-related complications than if the procedure were performed during standard clinical practice.

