14.2 Adverse Event Collection Period

All AEs, non-serious AND serious, must be reported by the clinical site investigator(s) from randomization through Day 30. Only SAEs must be reported through the end of the study period.

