14.4 Medical Safety Monitor

An Independent Medical Safety Monitor has been appointed to review all serious adverse events (SAEs) reported during the study. The MSM will adjudicate the relationship of the SAE to both the study intervention and the principles and intensity of overall care as described in the protocol as well as enter the expectedness of the reported SAE. In addition, the MSM will regularly review aggregated AE data (provided by the SDCC). The MSM will present any concerns regarding safety to the Study Executive Committee and the DSMB Liaison.

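### The SAE definition in Section 14.1 omits life-threatening and other medically important events, so one resolved without in-patient admission or lasting disability is non-serious and, after Day 30, need not be reported as an AE.

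*Combined protocol and SAP*

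**What the plan says.** Section 14.1 opens its definition with "A Serious Adverse Event (SAE) is any adverse event that results in any of the following" and lists four items, lettered a to d without a gap:

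- item (a) is that the subject dies;
- item (b), on hospital stays, is worded "In-patient hospitalization (for reasons other than observation) or prolongation of an existing hospitalization";
- item (c), on lasting harm to function, is worded "A persistent or significant disability or incapacity";
- item (d), the last, covers defects present at birth.

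Section 14.2 sets the collection window. First, "All AEs, non-serious AND serious, must be reported by the clinical site investigator(s) from randomization through Day 30". After that, "Only SAEs must be reported through the end of the study period".

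Section 14.4 provides the independent case review: "An Independent Medical Safety Monitor has been appointed to review all serious adverse events (SAEs) reported during the study". The same section has the Monitor judge relatedness and expectedness for those events, and look at pooled AE data at intervals. Section 14.5 gives the DSMB cumulative safety data at least twice a year.

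**The concern.** Seriousness decides two things in this plan: whether the Medical Safety Monitor sees an event as an individual case and, after Day 30, whether the site must file an AE report. The definition therefore has to catch events that are grave when they happen, not only those that end in death, admission or disability.

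As written, it does not. A subject could come close to dying, be treated and sent home, and the event would be non-serious.

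At stake is oversight of harm in a trial whose stated purpose includes weighing the risk of ERCP against its benefit. Rare grave events are few in a trial of 234, so each matters to those who monitor safety. The primary endpoint and its analysis are not affected.

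**Working it through.** There is no design figure to reproduce. The check is to follow one event through the sections, and then to see how much of follow-up falls under the narrower reporting rule.

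**1. Is the event serious?** Take a life-threatening event treated in an emergency room, with the subject discharged and well. It is not death, in-patient admission or a birth defect. It meets item (c) only if it leaves persistent or significant disability or incapacity. If not, it is non-serious. No other section adds a life-threatening, medically important or intervention-required criterion. Section 14.1 names CTCAE for AE reporting, but nothing in the document ties a CTCAE grade to seriousness.

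**2. Does an observation stay count?** Item (b) can be read in two ways.

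- If observation means a hospital status that is not in-patient, any event handled under that status fails item (b), whatever was done during the stay.
- If it means an admission made only in order to watch the patient, an overnight in-patient stay for treatment passes.

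The text does not settle which is meant. The emergency-room case in step 1 fails on either reading.

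**3. What follows from being non-serious?**

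| When | AE report (14.2) | Case-level review by the Monitor (14.4) |
|---|---|---|
| Randomization to Day 30 | Required | No; pooled data only |
| After Day 30 | Not required | No |

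**4. How much of follow-up lies after Day 30?** Section 5.4 gives follow-up of 6 to 48 months. The share under SAE-only reporting is 1 − 30 / (days of follow-up):

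- 6 months: 1 − 30/183 = 84%
- 12 months: 1 − 30/365 = 92%
- 48 months: 1 − 30/1461 = 98%

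These are shares of time, not of events.

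**5. Does the protocol itself create exposure in that period?** Yes. Section 9.4.2 schedules an MRI/MRCP at about 18 months with gadolinium, and with secretin where available. Section 11 lists allergic reaction as a risk of both agents. A severe reaction treated on the spot and discharged would not be a reportable AE, although the study ordered the scan. Section 9.6 also foresees ERCP during follow-up.

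**6. Are there other routes into the data?** Under Section 9.4.3 the semiannual calls ask about hospital stays, emergency-room visits and new diagnoses, and sites can review the answers. Under Section 5.1, pancreatitis and pancreas-related pain events get their own documentation; Section 2 defines a pain event so as to include emergency-room evaluation. An event may therefore reach the database. But a call may come up to about six months after the event, and Section 9.4.3 then asks the site to document those AEs that are reportable, which leads back to Section 14.2.

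**The case against.** The best case on the other side is that the practical loss is small, and much of it stands.

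- **Procedure complications mostly fall in the full-reporting window.** Section 11 gives hemorrhage at 1–2% and perforation at under 1%. With 117 subjects per arm that is 117 × 0.01 to 117 × 0.02 = 1.2 to 2.3 hemorrhages and fewer than 117 × 0.01 = 1.2 perforations. A reader might infer that one or two such events would drop out of SAE review, and that this would be a large share of the serious harm other than pancreatitis. The documents do not support that. Nothing places these complications after Day 30, no fraction managed without admission is given, and there is no total of expected SAEs to serve as denominator.
- **The dominant harm is caught.** The high-risk language in Section 3.5 concerns post-ERCP pancreatitis. The trial's definition of that event requires at least two days in hospital, which would ordinarily meet item (b).
- **Seriousness is not the only way to be seen.** The Monitor and the DSMB also receive pooled safety data, and the routes in step 6 exist. A reader might infer that a missed event vanishes from the trial; it need not. But pooled AE data cannot show a late event that was never collected as an AE.
- **The observation clause is ambiguous.** It would go too far to say that classification depends on each hospital's observation policy; that follows only on one reading.
- **The Month 18 scan gives no count either.** With even accrual over 42 months and a 48-month maximum, subjects enrolled in the first 48 − 18 = 30 months reach that visit: 234 × 30/42 = 167. This is before dropout, deferral for a recent scan, and sites without secretin, and Section 11 gives no rate of severe allergic reaction to multiply by.

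Section 5.1 also refers to a Manual of Procedures, which is not among the documents and might refine the criteria. None of this supplies the missing criteria in the protocol.

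**Conclusion.** The point holds as a gap in a stated rule. The SAE list is closed and has no life-threatening or medically important criterion. An event of that kind that ends without death, in-patient admission or disability under item (c) is non-serious. Up to Day 30 the loss is individual adjudication by the Medical Safety Monitor. After Day 30 the loss is the AE report itself.

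This rests on reading the four items as complete, which their wording and lettering support. Including observation stays in the gap depends on one of two readings of item (b); the emergency-room case does not.

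The number of events affected cannot be estimated from the documents, and the case for change does not depend on it. It rests on the kind of event left outside safety reporting.

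**What to change.** In Section 14.1 and on the AE case report form, add two criteria:

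- (e) the event was life-threatening;
- (f) an important medical event that required medical, endoscopic or surgical intervention to prevent one of the listed outcomes.

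Reword item (b) so that it is clear whether observation refers to hospital status or to the purpose of the admission. State that an observation stay does not make an event non-serious when (e) or (f) applies. If the Manual of Procedures already carries wider criteria, bring them into Section 14.1 so that the two agree.

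The cost is a few lines of text, a change to the form's pick-list, and a few more SAE reports for sites and the Monitor. Sample size, endpoints, analysis and clinical care are unchanged.

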14.2 Adverse Event Collection Period

All AEs, non-serious AND serious, must be reported by the clinical site investigator(s) from randomization through Day 30. Only SAEs must be reported through the end of the study period.

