8.2 Eligibility Assessment

Any patient ≥ 18 years old who is believed to have iRAP and suspected pancreas divisum will be considered for inclusion in the study. Prior to approaching a potential subject regarding study participation, study staff may review the existing available medical

records for evidence of exclusion criteria. If no evidence of exclusion criteria is identified, the patient will be approached to discuss study participation.

As in all trials, the goal is to achieve a high level of compliance with protocol requirements by assuring, during the eligibility assessment, that the potential participant is fully informed and agrees to the protocol requirements. In addition, participants with a strong likelihood of non-adherence (e.g. for reasons such as difficulties in adhering to follow-up schedule) should not knowingly be enrolled. Adherence of the clinical center staff to careful assessment of the participant's understanding of the trial and a clinical center environment which supports the continued commitment of the participants are essential for the trial to be successfully completed.

Conditional Eligibility: Once a subject has agreed to study participation and informed consent has been obtained and documented, research personnel begin screening procedures required to determine conditional eligibility. Full eligibility for this trial cannot be assessed until EUS is performed immediately prior to randomization.

The following will be performed to assess conditional eligibility:

- The TWEAK alcohol screening test will be administered. A score of < 4 is required for study eligibility.
- Records of at least two previous attacks (including laboratory results and/or imaging studies) must be obtained and reviewed to determine if the attacks meet inclusion criteria.
- Films from a clinically indicated MRCP procedure must be reviewed with a radiologist at the recruiting site to confirm pancreas divisum, rule out definitive changes of calcific chronic pancreatitis, and to rule out other etiologies of acute pancreatitis. The MRCP procedure is performed as part of standard of care and will not be performed specifically for research purposes.
- Study personnel will interview the subject and review medical records to confirm remaining eligibility criteria.

Pre-Randomization Screening Procedures:

Additional procedures required to determine eligibility must be performed immediately prior to and during EUS at the Randomization/Treatment visit.

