9.3 Observational cohort

In addition to randomized subjects, we plan to enroll approximately 100 patients with iRAP and pancreas divisum who refuse randomization, those who refuse ERCP, or those in whom ERCP is not recommended by the blinded physician investigator into an observational cohort. These subjects will be followed for subsequent acute pancreatitis episodes, systematic, semiannual assessments for patient-centered outcomes, and clinical (observational) assessments for the interval development of chronic pancreatitis and exocrine or endocrine insufficiency. Subjects in the observational cohort will undergo follow-up imaging and laboratory testing (including pregnancy testing) at the discretion of the treating physician(s).

Subjects enrolled into the observational cohort will follow the same follow-up schedule as patients who are randomized, with the following exceptions:

- No study-specific MRI/MRCP, and assessment of diabetes (endocrine) or exocrine insufficiency will be performed at 18 months. Therefore, these visits do not have to be in-person.

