9.4 Follow-up Procedures

The goal of the study is to achieve complete and accurate follow-up until completion of the trial. Appropriate compliance strategies should be implemented at clinical centers to encourage and support participants in protocol adherence. The ultimate success of this trial will depend upon the timely submission of complete and accurate data on all follow-up forms.

The Day 30 and 18-month follow-up visits will be completed as in-person, by telephone, or by virtual visits at the enrollment site. Otherwise, planned semiannual study assessments will be completed by a blinded central coordinator with the assistance of blinded site coordinators on an as-needed basis. Central follow-up will be performed in a confidential manner, so that personal health identifiers required to complete remote follow-up visits will be stored separate from the SHARP database.

9.4.1 30-day follow-up

Blinded study personnel will direct the 30-day follow-up encounter, which will occur at the enrolling site, over the telephone or virtually. All randomized subjects will undergo an abdominal X-ray during this visit which is typically performed as part of clinical care to confirm spontaneous passage of a pancreatic stent. While subjects randomized to EUS + Sham

will not have a pancreatic stent placed into the pancreatic duct, subjects in both groups will undergo an abdominal x-ray in order to maintain the blind. If a patient reports abdominal pain and a CT scan is ordered as part of the standard of care, the results of the CT scan can be used to confirm a stent has not been retained.

If the stent is identified in the gastrointestinal tract but not in the pancreatic duct, the patient will not be notified; this reflects usual clinical care, since migrated stents in the small intestine or colon are not followed thereafter since their spontaneous passage is virtually assured. If the stent is identified in the pancreatic duct, removal will be performed as part of the subject's clinical care.

In addition, blinded study personnel will assess the subject for adverse events that may have occurred since randomization.

Development of post-ERCP pancreatitis will be an important assessment at the 30-day follow-up period. Post-ERCP pancreatitis will be defined per consensus guidelines(Cotton, Eisen et al. 2010):

- 1) New or increased abdominal pain that is clinically consistent with a syndrome of acute pancreatitis, and

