- 2) Amylase or lipase $\geq 3x$ the upper limit of normal at least 24 hours after the procedure, and
- 3) Hospitalization (or prolongation of existing hospitalization) for at least 2 days.

The diagnosis of post-ERCP pancreatitis will be made based on review of medical records including clinical notes, results of lab tests and imaging studies.

Subjects who develop post-ERCP pancreatitis will be managed per standard clinical practice by the unblinded physician investigator. After recovery, subjects will continue to be followed per study protocol.

9.4.2 18 Month Follow-up

At approximately 18 months post-randomization, subjects will undergo an MRI with intravenous contrast (gadolinium) and MRCP protocol with secretin (a pancreatic secretagogue) enhancement if available to assess for interval morphological and/or functional changes of chronic pancreatitis. Gadolinium may be withheld if the glomerular filtration rate is < 30 mL/minute) or allergy. If there is a contraindication to MRI, a pancreas protocol contrast-enhanced computed tomography (CECT) scan will be performed. These images will be interpreted locally; de-identified images will be stored on a central radiology server at MUSC for future ancillary studies. Each site will have their own methods for removing personal health identifiers including metadata, before submitting the films to the Statistical and Data Coordinating Center for storage. If an MRI/MRCP had been performed within 6 months of these study time points, and is considered to be of adequate quality, then a repeat scan will be deferred. Images of MRI/MRCP scans, if performed at other intervals during the follow-up period, and available, will also be sent to a central radiology

server. If the subject is pregnant at the 18-month encounter, the MRI will not be performed until post-partum.

If the subject has not already been diagnosed with diabetes mellitus, assessment for diabetes mellitus will be performed at the 18-month follow-up encounter (fasting or random blood glucose and hemoglobin A1c). If the subject has not been diagnosed with exocrine insufficiency, subjects will undergo fecal elastase testing at the 18-month follow-up encounter.

9.4.3 Telephone follow-up (6 months, 12 months, 24 months, 30 months, 36 months, 42 months, 48 months)

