Chromoendoscopy agents: The most common side effect of the proposed dye agents (Methylene Blue or Indigo Carmine) is abnormal urine color. Less common side effects include diarrhea, frequent urination, nausea and vomiting, stomach cramps and fever.

Magnetic resonance imaging (MRI) with magnetic resonance cholangiopancreatography (MRCP): Subjects will undergo an MRI with MRCP at month 18 during the follow-up period (depending on their enrollment date). Subjects who have a contraindication to MRI (subjects who have heart pacemakers, metal implants, or metal chips or clips in or around the eyeballs, artificial heart valves, metallic ear implants, bullet fragments, and chemotherapy or insulin pumps) will not participate in this component of the study. There are no side effects of an MRI scan.

Contrast Agent (Gadolinium): The contrast material used for an MRI exam, called gadolinium, does not contain iodine and is less likely to cause side effects or an allergic reaction. There is a risk of an allergic reaction, so subjects will be queried about a prior history of allergy to gadolinium, fish, or shellfish (since a prior reaction to these foods increases the risk of an allergy to gadolinium). In addition, gadolinium is excreted by the kidneys, so a serum creatinine level will be checked immediately prior to the MRI scan (glomerular filtration rate < 30mL/minute). Gadolinium contrast agents may increase the risk of a rare, but serious, disease called nephrogenic systemic fibrosis in people with severe kidney failure. Nephrogenic systemic fibrosis triggers thickening of the skin, organs and other tissues. There is no effective treatment for this serious, debilitating disease.

Secretin (administered during MRI/MRCP): Side effects from secretin are uncommon, but include flushing, nausea, vomiting, abdominal pain, upset stomach, diarrhea, and a remote (less than 1 in 100) chance of acute pancreatitis. There is also a chance of an allergic reaction. Contrast-enhanced computed tomography scan (CECT). In subjects with a contraindication to MRI, a pancreas protocol CECT will be performed at month 18. The radiation exposure from one CECT (average dose = 10mSv) is roughly equivalent to the amount of radiation exposure one experiences from our natural surroundings in 3 years.

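### The adverse event window in section 14.2 misses events during the pre-randomization EUS and its anesthesia, and non-serious reactions to the study-specific Month 18 imaging

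*Combined protocol and SAP*

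**What the plan says.** Section 14.2 sets the reporting window in two sentences: "All AEs, non-serious AND serious, must be reported by the clinical site investigator(s) from randomization through Day 30", followed by "Only SAEs must be reported through the end of the study period". The Day 30 visit in section 9.4.1 uses the same starting point: "blinded study personnel will assess the subject for adverse events that may have occurred since randomization".

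Two study procedures lie wholly or partly outside that window.

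- **Before it opens.** Section 8.2 says "Full eligibility for this trial cannot be assessed until EUS is performed immediately prior to randomization". Section 9.2 places randomization during the endoscopy session and performs any ERCP under the anesthetic already in use for the EUS. Subjects found ineligible at EUS return to standard care and are not randomized.
- **After the non-serious part closes.** Section 9.4.2 says "At approximately 18 months post-randomization, subjects will undergo an MRI with intravenous contrast (gadolinium) and MRCP protocol with secretin (a pancreatic secretagogue) enhancement if available", with contrast-enhanced CT if MRI is contraindicated. Section 9.3 shows that this imaging is a research procedure by exempting the observational cohort: "No study-specific MRI/MRCP, and assessment of diabetes (endocrine) or exocrine insufficiency will be performed at 18 months".

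Section 11 warns subjects of the risks of both. For EUS it gives perforation below 0.1% and sedation-related cardiopulmonary complications of 0.1-0.5%. For secretin it lists flushing, gastrointestinal symptoms, allergy and "a remote (less than 1 in 100) chance of acute pancreatitis". For gadolinium it lists allergic reaction.

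**The concern.** The protocol tells subjects about reactions to procedures done under study consent, but does not require sites to record all of them. A non-serious contrast or secretin reaction at Month 18 need not be entered as an adverse event. It would then be missing from the aggregated data that the Medical Safety Monitor reviews (section 14.4) and from the safety reports to the DSMB (section 14.5).

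The early gap is narrower in time but wider in kind. The start at randomization applies to serious events as well, so even a serious EUS complication in a consented subject who is then excluded falls outside the written requirement.

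What is at stake is a complete safety account of the trial's own procedures. The primary treatment comparison is not at stake.

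**Working it through.** The plan states no figure on this point, so there is nothing to reproduce. The check sets the reporting window against the order of study procedures, then puts bounds on exposure.

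**Step 1. Order of events against section 14.2**

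| Step | Source | Non-serious AE required? | SAE required? |
|---|---|---|---|
| Anesthesia and EUS, onset before randomization | 8.2, 9.2 | No | No |
| Same, subject excluded at EUS | 9.2 | No | No |
| Randomization to Day 30 | 14.2, 9.4.1 | Yes | Yes |
| Month 18 imaging | 9.4.2 | No | Yes |

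The second sentence of 14.2 gives no start date for serious events. The first puts their start at randomization, and no other section opens a window earlier or around Month 18. Section 9.4.1 contains an adverse event assessment; section 9.4.2 does not.

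**Step 2. What counts as serious**

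Section 14.1 lists death, inpatient admission or prolonged admission (observation stays excepted), disability, and congenital anomaly. It has no life-threatening or important-medical-event criterion. An acute allergic reaction at Month 18 that is treated and observed without inpatient admission, and leaves no lasting disability, is therefore non-serious under this list and need not be reported.

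**Step 3. What is captured by another route**

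- Acute pancreatitis after Day 30 is the primary endpoint (12.1), and all episodes count for Aim 2 (12.2). The definition does not require admission.
- Pancreatitis-type pain evaluated in an emergency room or hospital meets the pain-event definition (sections 2 and 9.6). Section 5.1 requires adverse event documentation for both pancreatitis and pain events.
- The calls in 9.4.3 ask about hospitalizations, emergency visits and new diagnoses. The next one after the imaging is at Month 24. Sites then document the adverse events that are reportable, which leads back to 14.2.

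**Step 4. Exposure at Month 18 (upper bound)**

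Inputs: N = 234 (15.1); 3.5 years = 42 months of enrollment and follow-up of 6 to 48 months (5.4). Assumption: uniform accrual. Section 9.4.3 gives a one-year minimum instead; I use 5.4 because 48 - 42 = 6.

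- Share reaching Month 18 = (48 - 18)/42 = 30/42 = 0.714.
- Subjects = 0.714 × 234 = 167.

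This is an upper bound. Secretin is given only where available, gadolinium may be withheld, a scan is deferred if an adequate one was done within 6 months, and attrition is ignored. The imaging falls 18 - 1 = about 17 months after the non-serious window closes. No rate is given for the minor or allergic reactions, so the expected number lost cannot be calculated.

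**Step 5. Events around the EUS (illustration)**

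At the 0.1-0.5% cardiopulmonary risk in section 11, for 234 randomized subjects:

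- Expected events = 234 × 0.001 = 0.23, to 234 × 0.005 = 1.17.
- P(at least one) = 1 - 0.999^234 = 21%, to 1 - 0.995^234 = 69%.

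For randomized subjects these are upper values for the gap, since only events starting before randomization are missed. Subjects excluded at EUS would add to the gap; their number is not given.

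**The case against.** The strongest reply is that this is a reasonable choice: collect everything for 30 days after the randomized procedure, then serious events only. Month 18 imaging serves exploratory Aim 4 and is scheduled alike in both arms, and the safety of secretin or gadolinium is not a trial objective. Section 11 calls EUS routine for these patients. Section 14.2 sets a minimum and does not stop sites from reporting more. Section 5.1 also points to a Manual of Procedures that is not among the documents and might cover imaging reactions.

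Much of this stands. The gap does not bias the randomized comparison, and serious Month 18 reactions remain reportable to the end of the study. For randomized subjects the early gap lasts only from the start of anesthesia to allocation. The statement has to be that these events need not be reported, not that they will never be known. Against that, EUS here is the final eligibility step under study consent, and the Month 18 scan is described as study-specific, so both are the trial's responsibility.

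A reader might go further and multiply the stated ceiling of 1 in 100 by 167 subjects to infer up to about 1.7 secretin-related pancreatitis cases lost unless hospitalized. The documents do not support that. Those episodes are primary or Aim 2 outcomes whether or not the subject is admitted: subjects are told to contact the site, hold a standing laboratory order, and are assessed by a blinded investigator (9.4.4, 12.1).

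**Conclusion.** The point holds for two groups of events:

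1. Adverse events, serious or not, that start during the study EUS or its anesthesia before randomization, including all such events in consented subjects excluded at EUS.
2. Non-serious reactions to the Month 18 imaging other than pancreatitis and emergency- or hospital-evaluated pancreatic pain. These include allergic reactions managed without inpatient admission.

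The number of Month 18 reactions affected is unknown. At most about 167 of 234 subjects are exposed, if accrual is uniform. The conclusion rests on the protocol text and assumes that no document outside the review set adds a window. Severity is minor: this is a cheap improvement to safety reporting, with no effect on the endpoint, power or treatment comparison.

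**What to change.** In section 14.2:

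- Start AE and SAE reporting no later than induction of anesthesia for the study EUS, and state that this includes consented subjects then excluded at EUS. Align the Day 30 look-back in 9.4.1 with that start.
- Add a short window for all AEs, serious or not, after the Month 18 study imaging, whether MRI/MRCP or CT. The sponsor should set its length, since the documents give no basis for a particular number of days.
- Add one adverse event prompt to the Month 18 case report form.

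The cost is a small text change, one form field and a small extra reporting load at sites, including for subjects excluded at EUS. Treatment, endpoints and sample size do not change. If the Manual of Procedures already covers these windows, a cross-reference in 14.2 is enough.
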